## **Non-Operative Management and Early Response Assessment in Rectal Cancer (NOM-ERA)**

### **Protocol Revision History**

Initial Approval Version	04/01/19
Amendment #1	05/11/19
Amendment #2	03/17/20
Amendment #3	10/20/20
Amendment #4	03/16/21
Amendment #5	05/06/21
Amendment #6	10/08/21
Amendment #7	05/23/22
Amendment #8	02/07/23
Amendment #9	10/25/23
Amendment #10	09/15/25

**Primary Objective**

To determine the clinical complete response (cCR) rate of patients with Stage I-IIIB (cT1-3, N0-2a, M0) rectal cancer being treated with sequential short course radiotherapy followed by multi-drug chemotherapy.

**Secondary Objectives:**

1. To determine the 2 year progression free survival (PFS)
2. To determine the incidence of any grade  $\geq 3$  toxicity during treatment
3. To determine the incidence of post chemoradiotherapy grade  $\geq 3$  toxicity at 1 year
4. To determine quality of anorectal function at 1 year using the FACT-C questionnaire
5. To determine the 1 and 2 year organ preservation rate

## 1 BACKGROUND

### 1.1 Stage I-III Rectal Cancer

With the exception of a small group of favorable risk stage I disease, the standard of care for stage I-III rectal cancer usually includes a total mesorectal excision (TME). TME in the form of an abdominoperineal resection (APR) results in a permanent stoma, which may significantly impact the patient's self-image and quality of life (QOL). TME in the form of a low anterior resection (LAR) obviates the need of an ostomy but is associated with poorer rectal function.

There are increasing data supporting the use of chemotherapy and radiation therapy for non-operative management of rectal cancer. Habr-Gama et al. treated 183 distal rectal cancer (T2-4 N0-2) patients with 50.4-54 Gy in 30 fractions and concurrent 5-fluorouracil (5FU)/leucovorin and demonstrated an initial complete clinical response (cCR) of 49% patients 69% demonstrating a sustained cCR at 5 years. Appelt et al. treated 55 patients (T2-3 N0-1) with 60 Gy in 30 fractions with a 5 Gy brachytherapy boost plus oral tegafur-uracil. They reported 78% cCR with 16% local recurrence at 1 year with all local recurrences occurring within 2 years at the time of study publication. Maas et al. found that patients with cCR after neoadjuvant chemoradiation therapy have similar oncologic outcomes to those with pathologic complete response (pCR). The radiation in these trials was delivered over 5-6 weeks of daily treatment.

### 1.2 Short Course Radiation Therapy

Short course radiation therapy delivered as 25 Gy in 5 fractions is routinely used as preoperative therapy in Europe and Australia. The first Polish rectal study demonstrated that patients with T3-4 resectable rectal cancer treated with 25 Gy in 5 fractions followed by surgery versus 50.4 Gy in 28 fractions with concurrent 5FU followed by surgery had similar local recurrence (9% vs 14%), disease free survival (58% vs 56%) and overall survival (67% vs 66%). There was no difference in severe late toxicity (10% vs 7%). The second Polish rectal trial demonstrated that there was no difference in R0 resection and pCR rates in patients with T3-4 rectal cancer treated with 25 Gy in 5 fractions followed by FOLFOX then surgery compared to 50.4 in 28 fractions with FOLFOX followed by surgery. There was even a 3 year overall survival advantage for short course radiation (73% versus 65%), but the reason for this survival advantage in light of a non-significant difference in disease free survival is unclear. Important to note is that the dose prescribed with pre-operative short course radiation (5 Gy x 5 fractions) has a biologic effective dose (BED) of 37.5 Gy ( $\alpha/\beta=10$ ) in contrast to the BED of 63.7 Gy when 54 Gy is given in 30 daily fractions. Increasing the radiation dose to the tumor may further increase the clinical complete response (cCR) rate and allow for non-operative management.

### 1.3 Addition of Chemotherapy

There are increasing data to support increasing the interval from radiation to surgery. The

pCR rate of standard short course radiation followed by surgery 1 week later is approximately 1%. Increasing the interval to surgery from 2 to 6-8 weeks may increase the pCR rate without compromising oncologic outcomes. The Lyon R90-01 trial demonstrated that patients with T2 rectal adenocarcinoma treated with 39 Gy in 13 fractions had increased pCR if surgery is delayed to 6-8 weeks post-radiation versus 2 weeks post-radiation (26% vs 10%). In the non-inferiority Stockholm III, which evaluated short course radiation followed by surgery at 1 versus 4-8 weeks versus long course radiation therapy, there were no differences in long term cancer outcomes between the three treatment groups. The GRECCAR-6 trial showed that increasing the interval from chemoradiation to surgery from 7 to 11 weeks did not improve pCR. However, chemotherapy was not used during the interval between treatments. The Timing study provides evidence that extending the time from radiation to surgery with 3 months of chemotherapy increased pCR rates compared to observation and 1-2 months. Thus increasing the interval from radiation completion to surgery, especially with chemotherapy, may improve treatment outcomes.

In a phase II trial for patients with cT3-4, any N, any M rectal cancer recently completed at Washington University evaluating short-course radiotherapy followed by 4 cycles of FOLFOX chemotherapy (5FU, oxaliplatin, and leucovorin), a pCR was seen in 25% of patients. Mean prospective Functional Assessment of Cancer Therapy-Colorectal (FACT-C) scores for all five categories were not significantly different for pre-treatment ( $20.6 \pm 5.6$ ), pre-surgery ( $20.2 \pm 5.4$ ), or post-surgery time points ( $20.0 \pm 5.4$ ). Improved patient-reported functional outcomes were observed for patients undergoing sphincter sparing surgery, compared to those requiring an abdominoperineal resection with ostomy. In patients with an ostomy, FACT-C scores for functional well-being 1-year post-surgery were significantly reduced (lower QOL) compared to patients without ostomy (13.2 vs 19.2). Thus despite the side effect profile associated with radiation and chemotherapy, it may provide improved QOL over the sequelae associated with an ostomy and permanent stoma.

#### **1.4 Rationale**

Our phase I trial of short course radiation therapy followed by chemotherapy showed 74% cCR. Given the promising response rate, we are evaluating short course radiation therapy (SCRT) followed by chemotherapy in a multi-institution phase II trial to validate the cCR rate of this treatment paradigm. SCRT has not been prospectively evaluated in non-operative management for patients with non-metastatic rectal adenocarcinoma.

#### **1.5 Correlative Background**

In contrast to the parallel technologies that guide the management of breast or prostate cancer, there are no clinically implemented biomarkers that predict or prognosticate outcomes for rectal cancer. Colorectal cancer metastatic potential and aggressive proliferative phenotype have been linked to its tumor microenvironment. Cancer-associated fibroblasts (CAFs) deposit extra-cellular matrix (ECM) proteins resulting in a dense fibrotic stroma that may confer resistance to chemotherapy, potentiate aggressive

phenotype and limit infiltration and function of anti-tumor immune cells. FAK expression is associated with poorer survival in colorectal cancer patients after chemoradiation and is also associated with fibrosis and poor patient outcomes in pancreas adenocarcinoma.

Cell-free DNA is emerging as a powerful method for quantitating tumor disease burden noninvasively. Recently, the Vogelstein group at Johns Hopkins University measured circulating tumor DNA (ctDNA), the tumor component of cell-free DNA, in colorectal cancer patients treated with surgery and chemotherapy and demonstrated robust ability to measure molecular residual disease which was highly prognostic. Similar data are now available in breast cancer, lung cancer, cervical cancer, and pancreatic cancer. While the majority of this data is in the setting of surgery, Chaudhuri et al. demonstrated that ctDNA can also be measured before and after radiotherapy +/- chemotherapy for lung cancer, with post-treatment molecular residual disease (MRD) detection correlating significantly with eventual disease progression. In preliminary data, Chaudhuri et al. further showed that mid-treatment ctDNA quantitation during chemoradiation may be prognostic for lung cancer patients. Given these data, our goal is to measure circulating tumor DNA pre-, during and post-treatment as part of rectal cancer nonoperative management and correlate our findings with clinical and radiographic outcomes.

## 2 OBJECTIVES

Objectives	Endpoints	Justification for Endpoints
Primary		
To determine the clinical complete response (cCR) rate of patients with stage I-IIIB (cT1-3, N0-2a, M0) rectal cancer being treated with sequential short course radiotherapy followed by multi-drug chemotherapy.	cCR at completion of short course radiation therapy and chemotherapy	Nonoperative management treatment paradigms must be effective at eliciting a clinical complete response.
Secondary		
1. To determine the 2 year progression free survival (PFS) 2. To determine the incidence of any grade $\geq 3$ toxicity during treatment. 3. To determine the incidence of post chemoradiotherapy grade $\geq 3$ toxicity at 1 year 4. To determine quality of anorectal function at 1 year	1. PFS at 2 years 2. Incidence of any grade $\geq 3$ toxicity during treatment 3. Incidence of post chemoradiotherapy grade $\geq 3$ toxicity 4. Quality of anorectal function as measured by the FACT-C questionnaire at 1 year	1. Important to assess disease recurrence, metastasis and death when implementing new treatment paradigm. 2. Important to assess acute toxicity as there is concern that short course radiation is associated with significantly more acute toxicity.

using the FACT-C questionnaire.
 
5. To determine the 1 and 2 year organ preservation rate
	
5. Organ preservation rate at 1 and 2 years
	
3. Important to assess toxicity with new treatment paradigm, especially if rectum is not resected for nonoperative patients.
 
4. Treatment cannot be so toxic that even with preserved rectum patient QOL is poor.
 
5. Patients with cCR may still have regrowth of primary resulting in surgery. Need to assess how many patients can keep their rectum.

Tertiary/Exploratory		

1. To associate tumor microenvironment (including FAK expression) with cCR and other clinical outcomes.
 
2. To associate ctDNA levels with cCR and other clinical outcomes.
		

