### **5 EVALUATION STUDIES**

#### **5.1 Pre-treatment**

Within 12 weeks of day of simulation for RT but no later than the first radiation treatment:

- Examination by treating surgeon, medical oncologist, and radiation oncologist
- CBC with diff, CMP, CEA
- Staging study to evaluate extent of disease in the chest, abdomen and pelvis: CT w/ contrast is preferred to rule out metastatic disease

- Rectal protocol MRI pelvis to assess the local extent of the primary tumor, including T and N stage.
- Pregnancy test (for women of childbearing potential) – within 14 days of first treatment
- Colonoscopy (within 6 months is acceptable)
  - If feasible it is strongly recommended that the following physical findings should be scored:
    - Tumor location (distance in cm from the anal verge to the distal tumor margin)
    - Circumferential lesion Y/N
- Research biopsy (see Section 11.1)
- Blood for ctDNA (see Section 11.2)
- FACT-C quality of life questionnaire

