### 18.5 Data Analysis

Demographic and clinical characteristics of the sample will be summarized using descriptive statistics. Primary endpoint of the cCR rate will be reported as a proportion with 95% confidence interval (CI), and a one-sided asymptotic Wald test will be performed

to compare the study cohort cCR rate to the null value of 30%. PFS is defined as the time from date of treatment to death or progression, which occurs first. The alive patients without progression are censored as the last date follow-up. Kaplan-Meier method will be used to calculate PFS at 2-year. Proportions of any grade  $\geq 3$  toxicity during treatment, of post chemoradiotherapy grade  $\geq 3$  toxicity and organ preservation rates at 1 and 2 year will be calculated. Their corresponding 95% CIs will also be provided. The quality of anorectal function as measured by the FACT-C questionnaire is collected at screening, completion of chemo, and 1 year after RT. The generalized estimating equation (GEE) model with appropriate link function will be used to analyze this longitudinal data, in which the correlation among the repeated measures from the same patient need be considered. The autoregressive of first order as working correlation structure will be used and the patients with missing values at any time points will be excluded from GEE analysis. Least square means for quality of anorectal function at 1 year after RT will be estimated and 95% CI calculated within the use of GEE sandwich method when accounting for within-patient correlation.

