### FACT-C (Version 4)

Below is a list of statements that other people with your illness have said are important. **Please circle or mark one number per line to indicate your response as it applies to the past 7 days.**

PHYSICAL WELL-BEING		Not at all	A little bit	Some-what	Quite a bit	Very much
GP1	I have a lack of energy .....	0	1	2	3	4
GP2	I have nausea .....	0	1	2	3	4
GP3	Because of my physical condition, I have trouble meeting the needs of my family .....	0	1	2	3	4
GP4	I have pain .....	0	1	2	3	4
GP5	I am bothered by side effects of treatment .....	0	1	2	3	4
GP6	I feel ill .....	0	1	2	3	4
GP7	I am forced to spend time in bed .....	0	1	2	3	4

SOCIAL/FAMILY WELL-BEING		Not at all	A little bit	Some-what	Quite a bit	Very much
GS1	I feel close to my friends .....	0	1	2	3	4
GS2	I get emotional support from my family .....	0	1	2	3	4
GS3	I get support from my friends .....	0	1	2	3	4
GS4	My family has accepted my illness .....	0	1	2	3	4
GS5	I am satisfied with family communication about my illness .....	0	1	2	3	4
GS6	I feel close to my partner (or the person who is my main support) .....	0	1	2	3	4
Q1	Regardless of your current level of sexual activity, please answer the following question. If you prefer not to answer it, please mark this box  and go to the next section.					
GS7	I am satisfied with my sex life .....	0	1	2	3	4

Patient ID#: \_\_\_\_\_

Date of Completion: \_\_\_\_\_

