**FACT-C (Version 4)**

Please circle or mark one number per line to indicate your response as it applies to the past 7 days.

ADDITIONAL CONCERNS		Not at all	A little bit	Some- what	Quite a bit	Very much
C1	I have swelling or cramps in my stomach area .....	0	1	2	3	4
C2	I am losing weight.....	0	1	2	3	4
C3	I have control of my bowels.....	0	1	2	3	4
C4	I can digest my food well.....	0	1	2	3	4
C5	I have diarrhea (diarrhoea) .....	0	1	2	3	4
C6	I have a good appetite .....	0	1	2	3	4
C7	I like the appearance of my body .....	0	1	2	3	4
Q2	Do you have an ostomy appliance? (Mark one box)	 No	or	 Yes		
If yes, please answer the next two items:						
C8	I am embarrassed by my ostomy appliance .....	0	1	2	3	4
C9	Caring for my ostomy appliance is difficult .....	0	1	2	3	4

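### The FACT-C result is labelled anorectal function, but only 2 of the 34 items all patients answer concern the bowel, and Section 18.5 does not say which score is analysed

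*Combined protocol and SAP*

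**What the plan says.** Section 2 gives objective 4 the endpoint "Quality of anorectal function as measured by the FACT-C questionnaire at 1 year". Sections 18.1 and 18.4 and Appendix F carry the same label. The justification beside it in Section 2 is worded differently: "Treatment cannot be so toxic that even with preserved rectum patient QOL is poor". Section 5.1 lists the instrument as the "FACT-C quality of life questionnaire".

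Section 18.5 fits a GEE to FACT-C at screening, at completion of chemotherapy and about one year after radiotherapy. It then states: "Least square means for quality of anorectal function at 1 year after RT will be estimated". It names no total, section score or item. Section 18.6 takes the same undefined quantity as the outcome of linear regressions on the biomarkers.

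Appendix A reproduces the form: four well-being sections, then Additional Concerns, which contains "I have control of my bowels" (item C3). Question Q2 on the form asks about an ostomy appliance, and C8 and C9 are for patients who have one. Section 18.4 requires a baseline and at least one later FACT-C and does not mention ostomy status. The study calendar (Section 13) and the data schedule (Section 14) list no other bowel-function questionnaire.

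**The concern.** The named construct and the instrument do not match. In a trial meant to spare the rectum, readers will want to know whether the retained rectum works. A FACT-C mean published as anorectal function would be taken as the answer, although nearly all of its content lies elsewhere. A stable mean could be read as preserved function when bowel control had worsened, and a fall could be read as lost function when it came from mood or work.

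Two features add to this. The score is not named, so it could be chosen after the data are seen. And patients who have had a resection with an ostomy can enter the same mean as patients who keep the rectum, although bowel control has no clear meaning with a stoma.

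**Working it through.** The plan gives no sample size, effect size or standard deviation for FACT-C, so there is no stated figure to reproduce. The check is a count of items in Appendix A, each scored 0 to 4. Equal weights are assumed.

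**Items answered by all patients**

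| Section | Items | On bowel function |
|---|---|---|
| Physical well-being (GP1–GP7) | 7 | 0 |
| Social/family (GS1–GS7) | 7 | 0 |
| Emotional (GE1–GE6) | 6 | 0 |
| Functional (GF1–GF7) | 7 | 0 |
| Additional Concerns (C1–C7) | 7 | 2 (C3, C5) |
| All | 34 | 2 |

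The first four sections hold items such as "I am forced to spend time in bed" and "I am satisfied with my sex life". The functional section covers work, enjoyment, acceptance of illness and sleep, not the bowel.

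**Shares**

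- General well-being: 27/34 = 79.4%.
- Additional Concerns: 7/34 = 20.6%.
- Bowel function (C3, C5): 2/34 = 5.9% of items; 2 × 4 = 8 of 34 × 4 = 136 points.
- Bowel function within Additional Concerns: 2/7 = 28.6%; 8 of 28 points.

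**Sensitivity to what counts as a bowel item**

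- C3 alone: 1/34 = 2.9% of all items; 1/7 = 14.3% of Additional Concerns.
- Adding C1 (swelling or cramps): 3/34 = 8.8%; 3/7 = 42.9%.
- Adding C1 and C4 (digestion): 4/34 = 11.8%; 4/7 = 57.1%. These two are abdominal and digestive symptoms and do not describe how the anus or rectum works.

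**What each possible score could show**

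- Total: a two-point worsening on both C3 and C5, other items fixed, moves it by 4/136 = 2.9%. Best to worst on both moves it by 8/136 = 5.9%.
- Additional Concerns: the same changes move it by 4/28 = 14.3% and 8/28 = 28.6%, but five of its seven items (cramps, weight, digestion, appetite, body appearance) can move it in either direction.
- Any of the other four sections: no bowel item at all.

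**Other sources in the trial.** Section 10 tracks adverse events to one year after the start of radiotherapy but does not capture grades 1 and 2. Below grade 3, C3 and C5 are therefore the main systematic record of bowel function, and Section 18.5 reports neither on its own.

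**Ostomy.** Section 5.4 places the FACT-C visit at 10–14 months from the start of radiotherapy without restricting it to non-operative patients, and keeps resected patients in data collection. Nothing in Section 18.4 or 18.5 splits them out.

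**The case against.** The best defence is that FACT-C suits the purpose Section 2 gives for it, which is quality of life. On that view only the label is wrong, in an unpowered secondary endpoint of a single-arm study with no threshold attached. That largely stands. It limits the weight of the point and is why the questionnaire should stay. It does not remove the point, because Section 18.5 would still print a mean under the wrong name.

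Severe bowel toxicity would also be seen through the grade 3 or higher endpoints. That stands for severe events only.

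A reader might infer more than the documents support:

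- *That the plan analyses the 136-point total, so bowel items can move the result by at most 5.9%.* Section 18.5 names no score. The figure applies only to a total with all other items fixed; items on side-effect bother or enjoyment of life might well move too.
- *That FACT-C is almost entirely general quality of life.* By section it is 79%. The accurate statement is that 32 of 34 items (94%) do not concern bowel function.
- *That the group's earlier trial shows FACT-C to be insensitive.* Section 1.3 reports that "Mean prospective Functional Assessment of Cancer Therapy-Colorectal (FACT-C) scores for all five categories were not significantly different" (20.6, 20.2 and 20.0). Flat means are equally consistent with no true change, and the documents do not say how these were formed. The same section shows functional well-being separating patients with and without an ostomy at one year, 13.2 against 19.2.
- *That making Additional Concerns the GEE outcome would cure the problem.* Five of its seven items are not bowel function, and the section that separated the ostomy groups would leave the model.

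**Conclusion.** The point holds as a mismatch between the label and the measure, together with an unnamed score and unseparated ostomy patients. No total or section score of FACT-C, reported alone, can support a statement about anorectal function: bowel items are 5.9% of the whole form (2.9% to 11.8% across the counts above) and 29% of the most relevant section. Even on the widest count, where Additional Concerns reaches 57%, the added items are not anorectal function.

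This rests on the item count in Appendix A, equal item weights, and the judgement that C3 and C5 are the bowel items. It does not show that FACT-C is a poor quality of life measure. How many patients will have an ostomy at one year is not given, so the effect of pooling them cannot be sized. Section 18.2 says the study is not powered for secondary endpoints, and FACT-C plays no part in the primary design. The change should be made, but it does not threaten the trial's main conclusion.

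**What to change.** 1. Reword objective 4 and its endpoint, wherever they appear, as colorectal-cancer-specific quality of life by FACT-C.
2. In Section 18.5, name the FACT-C score that enters the GEE, and use the same score in Section 18.6. Choosing Additional Concerns is optional; if it is chosen, state that most of its items are not bowel function.
3. Report C3 and C5 separately at each time point, stating the direction of each item (a high answer is good on C3 and bad on C5). Describe them as the only patient-reported evidence on bowel function.
4. Show the 1-year results separately for patients with and without an ostomy (Q2 on the form), and interpret C3 and C5 only in those without. Q2 does not identify resected patients without a stoma, so give their number in the no-ostomy group.

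No new visit, patient or instrument is needed. The cost is a narrower claim and a few more descriptive results. Timing also matters: the protocol was first approved in 2019, accrual was planned for about 3 years (Section 18.7), and the latest amendment is dated September 2025, so FACT-C data may already be in hand. The change should be dated before those data are analysed, so that the choice of score cannot appear to be driven by the results.
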